Myelofibrosis results in extramedullary hematopoiesis, massive hepatosplenomegaly and fibrosis in the marrow and there are several major issues unique to it from transplant perspective. These include high incidence of graft failure and weak graft after transplant necessitating use of stem cell boost²² and organ dysfunction - particularly involving liver - leading to a high incidence of veno-occlusive disease and non-relapse mortality.⁴⁰ A safe agent that can reduce organomegaly and disease burden pretransplant may improve transplant outcome by improving engraftment, reducing organ toxicity and lowering relapse risk. Furthermore, it may allow more patients to become eligible for transplant by improving their performance status. A Jak 2 inhibitor might be the answer.

Jak 2 inhibitors and stem cell transplantation:

Discovery of Jak2 V617F mutation, which makes kinase constitutionally active in patients with myeloproliferative disorders led to development several targeted agents including Pacritinib to inhibit this pathway. Jak 2 is mutated in up 60% of patients with ET and MF and 98% of patients with PV. Even in patients without this mutation, this pathway is overactive. Ruxolitinib, a Jak2 inhibitor, is licensed by FDA for MF reduces splenomegaly, improves constitutional symptoms, and improves survival both in patients with and without Jak 2 V617F. Early data on its usage pre-transplant are conflicting with excellent outcome reported in some studies, but a possible higher complication rate reported in other study. This later study presented as an abstract is difficult to interpret, because complications reported are hard to differentiate from usual complications seen post-transplant. Pacritinib causes less myelosuppression than Ruxolitinib and may be superior to ruxolitinib as a pre-transplant agent to reduce organomegaly and to reduce the disease burden.

Pacritinib:

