4.0 Treatment Plan

4.1 The investigational agent for this study is Pacritinib.

- 4.1.1 Patients will start Pacritinib 200 mg po bid.
- 4.1.2 Patients can proceed to transplant after 60 days of starting Pacritinib but not more than 180 days.
- 4.1.3 Pacritinib will be stopped 21 days prior to starting preparative regimen for SOC Allo TP.
- 4.1.4 If for whatever reason a patient cannot pursue or receive SOC Allo TP, they will be able to continue treatment with Pacritinib until there is evidence of disease progression.
- 4.1.5 A patient will still be able to proceed to SOC ALLO TP if for any reason they cannot complete 60 days of treatment prior to transplant.
- 4.1.6 If a patient vomits or misses a dose, will continue treatment with the next scheduled dose. Missed doses and reason for non-compliance will be recorded.
- 4.1.7 Every effort should be made to avoid CYP3A4 inducers or inhibitors (see Appendix H) while patients are on pacritinib. If concomitant therapy with CYPsA4 inhibitors or inducers is medically necessary and there are no available or suitable substitutes, this should be documented in the patient's medical record and extreme caution taken with their continued use during the study duration.
- 4.1.8 Patients will document compliance of taking medication on a patient diary.

4.2 Treatment Interruption:

Safety parameters including AEs, hematology, and serum chemistry will be monitored according to the protocol. Pacritinib treatment may be withheld for up to 4 weeks due to drug-related toxicities. A longer recovery period may be allowed based on the toxicity, but must be agreed upon between the investigator and medical monitor. After treatment interruption, patients may resume the pacritinib treatment at the same dose level or at a reduced dose level. No dose re-escalation is allowed.

4.3 Pacritinib Dose Management Guidelines for Pacritinib-Related Nonhematologic Toxicities:

- 4.3.1 A maximum of 2 dose reductions is allowed. The first dose reduction will be a 100 mg reduction from the original dose. The dose will be reduced to 200 mg Q AM and 100 mg Q PM
- 4.3.2 The second dose reduction will be another 100 mg reduction and the dose will be reduced to 100 mg BID.
- 4.3.3 Once the dose is reduced, no re-escalation is allowed.
- 4.3.4 Dose management for nonhematologic toxicities is summarized in Table 3.

Table 3 Treatment Toxicity and Dose Management: Pacritinib-Related Nonhematologic Toxicities		

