6.0 Statistical Considerations

General

This will be a single-arm, Phase II study of pacritinib, fludarabine, and busulfan as a preparative

regimen in allogeneic stem cell transplantation in patients with myelofibrosis. The primary endpoint is progression-free survival (PFS) in patients undergoing matched related or at least 7/8 matched unrelated donor transplant. We will enroll at least 21 evaluable patients, defined as patients who undergo transplant with a matched related or at least 7/8 matched unrelated donor. Patients who do not have a suitable related or unrelated donor will come off study and may receive a transplant from a haploidentical donor. For this reason and because some patients may decide not to undergo transplant after starting the drug, we may need to enroll up to 40 patients to ensure that 21 are evaluable for our primary endpoint.

Endpoints

6.1 Primary End Point (Progression-Free Survival):

Progression-free survival is defined as the time of stem-cell transplant to the time of death or disease progression.

6.2 Secondary End Points:

Neutrophil Engraftment is defined as a sustained ANC \geq 0.5 x 10 $^{\circ}$ /L for 3 consecutive days and evidence of donor chimerism by D+28 (the first chimerism study will be done 3-4 weeks post-transplant).

Platelet Engraftment is defined as a sustained first of three consecutive laboratory values of platelet $\geq 20x109/L$ with no platelet transfusions administered for 7 consecutive days.

Non-relapse mortality is defined as death without disease progression.

Liver response will be defined by the change in the size of the liver measured below the coastal margin in the mid-clavicular line by palpitation.

Spleen response will be defined by the change in the size of the spleen measured below the coastal margin in the mid-clavicular line by palpitation.

Quality of life will be measured by the QOL FACT BMT.

Symptom score will be measured by the MPD symptom score.

Immune recovery will be measured by various cell subsets and cytokine levels.

Primary Graft Failure is defined as failure to achieve an ANC \geq 0.5 x 10 $^{\circ}$ /L for 3 consecutive days by day 28, with <10% cellularity on bone marrow biopsy and no evidence of donor chimerism.

Secondary graft failure is defined as a sustained declined of ANC <0.5 x 10°/L for 3 consecutive days after initial documented engraftment with no evidence of disease progression.

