Complete remission is defined as per response criteria defined by European Myelofibrosis network (Appendix G.).

Relapse will be recorded by the day of detection.

Overall Survival is defined as the interval between day of transplant and day of death.

Sample Size and Power

The historical 1-year PFS rate in this population is 61%. Our goal is to improve this to 80%. We expect to enroll patients over a 3-year period and follow all patients for 1 year after enrollment is complete. Under these assumptions, assuming exponentially -distributed PFS times, and using a one-sided exponential MLE test with a 5% Type I error rate, we will need 21 patients to have 80% power to detect an increase in 1-year PFS to 80%. We will provide the 1-year PFS rate along with a corresponding 95% interval and test the hypothesis that it is greater than 61% using an exponential MLE test. Only patients who undergo transplant with a matched related or at least 7/8 matched unrelated donor will be include in this analysis.

Secondary Analyses

We will use the Kaplan-Meier method to estimate the distribution of secondary time-to-event (TTE) endpoints overall survival, time to neutrophil engraftment, and time to platelet engraftment. We will use Cox regression analysis will be used to assess the association between TTE endpoints (including PFS) and clinical and disease covariates of interest. We will assess the cumulative incidence of non-relapse mortality (NRM) and disease relapse in a competing risks framework and use the method of Fine and Gray to fit regression models to these endpoints.

Liver and spleen response to pacritinib will be measured by the change in the size of each organ measured below the coastal margin in the mid-clavicular line by palpation and imaging.

Quality of life (QOL) will be assessed using the QOL FACT BMT, and symptom score will be assessed by the MPD symptom score. Changes in these over time will be analyzed by a generalized linear mixed model (GLMM) approach to account for intra-patient correlation.

For the immune studies, various cell subsets and cytokine levels will be assessed at several timepoints. GLMM or other appropriate statistical models will be fit to assess changes over time in these parameters and relationships with other endpoints.

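### Progression or death during the pacritinib lead-in counts in no planned PFS or survival analysis, because both clocks start at transplant and the primary test keeps only matched-donor recipients

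*Combined protocol and SAP*

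**What the plan says.** The primary objective (Section 1.0) is to compare PFS, with pacritinib added before standard transplant, against historical controls. Section 4.1 sets the lead-in: "Patients can proceed to transplant after 60 days of starting Pacritinib but not more than 180 days". Pacritinib stops 21 days before conditioning (4.1.3). A patient who cannot complete 60 days may still be transplanted (4.1.5).

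Section 6.0 fixes the clock and the population. On the clock: "Progression-free survival is defined as the time of stem-cell transplant to the time of death or disease progression". Overall survival is likewise counted from the day of transplant. On the population for the primary test: "Only patients who undergo transplant with a matched related or at least 7/8 matched unrelated donor will be include in this analysis".

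Enrolment allows for losses: "we may need to enroll up to 40 patients to ensure that 21 are evaluable for our primary endpoint". Two reasons are given. One is donor availability: "Patients who do not have a suitable related or unrelated donor will come off study and may receive a transplant from a haploidentical donor". The other is that "some patients may decide not to undergo transplant after starting the drug".

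For patients who take pacritinib and are not transplanted, the end of Section 6.0 promises a separate summary of safety and unspecified further data. Section 7 removes patients for unacceptable toxicity (7.1), progression (7.2) or lack of a qualifying donor (7.6), and describes no follow-up after removal. Section 8 collects adverse events during the pacritinib phase, and serious events from the first protocol intervention to 14 days after the last dose, with treatment-related ones reportable later.

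**The concern.** The experimental treatment is given before the clock starts. A patient who progresses, dies or becomes unfit on pacritinib never enters the population in which its effect on PFS is judged. The analysis therefore conditions on having come through the experimental treatment and still being a transplant candidate with a matched donor. It describes outcome after transplant in those who got there, which is narrower than the effect of adding pacritinib to the pathway.

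The historical cohort in Section 2.4 is also measured in transplanted patients, but no pacritinib lead-in is described for it, nor how its patients were selected before transplant. If the lead-in removes poor-risk patients who would have been transplanted promptly in the historical series, the comparison with 61% favours pacritinib.

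The Background also suggests that a pre-transplant agent could help because "it may allow more patients to become eligible for transplant by improving their performance status". With no planned report of the proportion reaching transplant, the trial would not even describe that.

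**Working it through.** **Inputs, all from the protocol.** At least 21 evaluable and up to 40 enrolled patients; benchmark 61% and target 80% for 1-year PFS, taken here as Section 6.0 gives them; one-sided 5% exponential MLE test; 80% power; 3 years of accrual plus 1 year of follow-up. No lead-in failure rate is given.

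**1. The plan's sample size.** Hazards per year: λ0 = −ln 0.61 = 0.494 and λ1 = −ln 0.80 = 0.223. With uniform accrual over 3 years and 1 further year, the probability of an observed event is p = 1 − (e^(−λ) − e^(−4λ))/(3λ), so p0 = 0.682 and p1 = 0.417. On the hazard scale:

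n = [(1.645 × 0.494/√0.682 + 0.842 × 0.223/√0.417)/(0.494 − 0.223)]² = 22.1, so 23.

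Other standard forms of the test give 18 to 24. Simulated power with 21 patients is about 82% for the log-hazard and score versions. The stated 21 is reproduced to within the choice of variant. The issue here is who is counted, not the size of n.

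**2. Patients outside the primary analysis.** 40 − 21 = 19, and 19/40 = 47.5%. This is a planning ceiling, not an expected loss.

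**3. Where a lead-in event is counted.**

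| Event before matched transplant | Primary PFS | Overall survival | Elsewhere in the plan |
|---|---|---|---|
| Progression, no transplant | Not counted | No start date | Separate non-transplant summary, content unspecified |
| Death before transplant | Not counted | No start date | Same summary; serious-event reporting if within its window |
| Toxicity, no transplant | Not a PFS event in any case | No start date | Adverse-event collection, Section 8 |
| Haploidentical transplant | Excluded | Off study | Read literally, in neither set: transplanted, but without a qualifying donor |

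The serious-event window closes 14 days after the last dose, while conditioning starts 21 days after pacritinib stops. At least 21 − 14 = 7 days before conditioning are thus covered only for treatment-related events.

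**4. Illustration, by assumption.** Let a share f of all starters progress or die before transplant, and let all others, including decliners and haploidentical recipients, reach the 80% target. The overall rate is 0.80 × (1 − f):

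| f | Failures among 40 starters | Overall rate |
|---|---|---|
| 0% | 0 | 80% |
| 5% | 2 | 76% |
| 10% | 4 | 72% |
| 20% | 8 | 64% |

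These figures mix clocks, because success is still counted one year after transplant. They show sensitivity to f and do not forecast a first-dose PFS rate.

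**The case against.** The primary analysis has a sound rationale. Both cohorts are measured from transplant, so the time origins match. A first-dose PFS rate has no comparator in the documents. The historical patients also had to reach transplant, so some selection exists on both sides. All of this stands, and it is why the primary analysis should stay.

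Three stronger readings are tempting, and the documents do not support them.

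- A reader might infer that lead-in harm is ignored. It is not: Section 8 collects pacritinib-phase adverse events, Section 6.0 promises a summary of non-transplanted patients, and those who stop pacritinib early can still be transplanted and analysed. The gap is in efficacy.
- A reader might treat the 19 exclusions as treatment failures. The protocol attributes them to lack of a donor and to patient choice; lack of a donor is not a failure of pacritinib.
- A reader might add failures to the 21 transplanted patients: with 17 of 21 progression-free (81%), four failures give 17/25 = 68% and seven give 17/28 = 61%, so the whole gain seems lost. That holds only if 25 or 28 patients started. With 40 starters, and the other exclusions assumed uninformative, the figures are (36/40) × (17/21) = 73% and (33/40) × (17/21) = 67%. Under the formula above, 61% is reached only at f = 1 − 0.61/0.80 = 23.75%, or 9.5 of 40, and even that sets unlike clocks side by side.

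It is also fair that wider transplant eligibility is a background suggestion, not a listed objective. With no control rate, a transplant-attainment percentage would describe that outcome without proving a benefit.

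**Conclusion.** The point holds for the planned PFS and overall survival analyses. Lead-in progression or death contributes to neither, and the separate summary does not repair this: it names no efficacy measure and, read literally, omits haploidentical recipients. The excluded share may reach 47.5% at the enrolment ceiling.

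A reader might go further and conclude that the comparison with 61% is shown to be biased by a known amount. The documents do not allow that. They give neither a lead-in failure rate nor the pre-transplant selection of the historical cohort, so bias in pacritinib's favour is plausible and of unknown size. The 76%, 72% and 64% rest entirely on assumed failure shares of 5%, 10% and 20%, and on the remaining patients reaching the target.

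This is a gap in what the trial can say about its own objective, not an error in the primary test. It should be closed before analysis, because follow-up data not collected after removal may not be recoverable.

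**What to change.** Keep the primary analysis as it is.

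- **Section 6.0, supportive analysis.** Add PFS and overall survival estimates with confidence intervals, from first dose, in all patients who take at least one dose of pacritinib. Count progression or death before transplant as events. Keep decliners and haploidentical recipients in the set. Add a sensitivity analysis that censors at haploidentical transplant, noting that such censoring may be informative. Do not test either result against 61%, because the time origin differs.
- **Section 6.0, accounting.** Report the number and percentage of starters who reach matched transplant. Tabulate one reason for each who does not: no donor, patient choice, progression, death, or toxicity or unfitness.
- **Section 7.** State that patients removed before matched transplant remain in follow-up for progression and vital status, subject to consent.

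No extra patients are needed. The cost is protocol and SAP wording plus modest follow-up of those who leave early; patients who continue pacritinib without transplant already attend monthly (4.1.4, 5.2). The drawback for the sponsor is that the supportive figure may be less favourable than the primary one.

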1.0 Objectives

Primary Objective:

To compare the progression-free survival of adding Pacritinib prior to standard of care allogeneic stem cell transplantation (SOC Allo TP) conditioning with Fludarabine and Busulfan AUC of 4000 microMol-min per day to historical controls in patients with myelofibrosis.

Secondary Objectives:

To evaluate safety and efficacy of this therapy as determined by:

- 1.1 Neutrophil and platelet engraftment.
- 1.2 Non-relapse mortality at one year post transplant.
- 1.3 Overall survival at one year post transplant.
- 1.4 Liver and spleen response to Pacritinib.
- 1.5 Immune recovery.
- 1.6 Quality of life and symptom score.
- 1.7 Primary and secondary graft failure.
- 1.8 Complete remission.
- 1.9 Relapse.

To evaluate the use of marrow specific quantitative MRI (qMRI) sequences in assessment of disease burden, including:

- 1.10 Diffusion-weighted imaging (DWI) with apparent diffusion coefficient (ADP) maps
- 1.11 Marrow fat quantification sequences

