5.0 Evaluation During Study

5.1 Disease Assessment Prior to Start of Pacritinib (baseline):

- a) Patient medical history and physical examination including measurement of liver and spleen size by physical examination or imaging (MRI or CT or ultrasound if possible) with addition of marrow-specific MRI sequences.
- b) CBC, differential and platelet count
- c) Bone marrow aspiration and biopsy
- d) Chemistry panel
- e) Serology for CMV, HBV, HCV and HIV
- f) B-HCG in women of childbearing potential
- g) 2 D echo, EKG
- i) Pulmonary function tests with DLCO
- j) Chest x-ray
- k) MF symptoms questionnaire (Appendix D.)
- I) Fact BMT questionnaire (Appendix E.)
- m) Blood for immunological profile if patient agrees to consent to optional study.

5.2 Follow up each month while on Pacritinib:

Patients will come to MDACC once each month to pick-up the next month's Pacritinib and have the following done. The monthly visits will continue as long as patient is taking Pacritinib.

- a) Medical history and physical examination
- b) CBC, differential and platelet count
- c) Chemistry panel
- d) EKG

Cycle 1 only: Day 14 (+/- 2 days) CBC, differential and platelet count and chemistry panel. These can be drawn locally and results sent to MDACC. The PI/treating physician must review outside lab results, determine clinical significance, sign and date the outside lab results.

Cycle 1 only: During week 2, study personnel will call patient about any new symptoms.

Patients treated on this protocol may require supportive care treatment (concomitant medications). These medications are considered standard of care and have no scientific contribution to the protocol; therefore no data will be captured on various medications needed or their side effects.

5.3 Within about 7 days after completion of Pacritinib (but before transplant):

- 1) Physical examination including measurement of liver and spleen size by physical examination or imaging (MRI or CT or ultrasound if possible).
- 2) EKG
- 3) Bone marrow aspiration and biopsy

5.4 Post-transplant Evaluations:

- 5.4.1 Post-transplant evaluations will follow our standard practice and are done to monitor engraftment and disease status.
- 5.4.2 Additional post-transplant follow-up specific to this study at approximately 1, 3, 6, and 12 months post-transplant:
 - 1) At around 3 months:
 - Measurement of liver and spleen size by physical examination or imaging (MRI or CT or ultrasound if possible).

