 - b) Bone marrow aspiration and biopsy

At around 12 months:

- a) Repeat measurement of liver and spleen size, if liver and spleen were still enlarged at 3 months post-transplant.
- b) Bone marrow biopsy aspiration and biopsy
- 2) Blood for immunological profile if patient agrees to consent to optional study.
- 3) MF symptoms questionnaire (Appendix D.)
- 4) Fact BMT questionnaire (Appendix E.)
- 5) Participant Follow-up Assessment questionnaire (Global Impression of Change Scale, Appendix F.)

5.5 Correlative Research Studies (Optional):

60 cc of blood (5 green top tubes and 1 purple top tube) will be collected before the first dose of pacritinib, after the last dose of pacritinib (before transplant), and at approximately 1, 3, 6, and 12 months post-transplant.

This research blood will be sent to [name] laboratory at MD Anderson. Studies to be conducted are described in Section 2.4.

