7.0 Criteria for Removal from the Study

- 7.1 Any toxicity that is deemed unacceptable by the study PI.
- 7.2 Disease progression.
- 7.3 Lack of compliance with the requirements of the study.
- 7.4 Withdrawal of consent.
- 7.5 After one year of transplant.

7.6 No matched related or less than 7/8 matched unrelated donor.

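### Quality of life and symptom scores rest on a mixed model alone, while removal at progression appears to stop the forms; the month-12 change is therefore undefined for patients who progress or die and may be too favourable.

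*Combined protocol and SAP*

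**What the plan says.** - Section 1.0 makes this a secondary objective: "1.6 Quality of life and symptom score".
- Section 5.1 lists both questionnaires at baseline. Section 5.3 (after pacritinib, before transplant) lists neither. Section 5.4.2 schedules them under "Additional post-transplant follow-up specific to this study at approximately 1, 3, 6, and 12 months post-transplant" and sets no condition about progression.
- The whole of the planned analysis, in section 6.0, Secondary Analyses, is: "Changes in these over time will be analyzed by a generalized linear mixed model (GLMM) approach to account for intra-patient correlation". The text supplied gives no missing-data assumption, no rule for death or progression, no completion table and no sensitivity analysis.
- The same section treats non-relapse mortality and relapse as competing risks. Nothing comparable is planned for the patient-reported scores.
- Section 7.0 lists among the criteria for removal "7.2 Disease progression" and "7.5 After one year of transplant".

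**The concern.** Accounting for correlation within a patient deals with repeated measures. It does not deal with why the measures stop. If forms end at progression, they go missing because of the outcome that the trial studies, since section 6.1 states: "Progression-free survival is defined as the time of stem-cell transplant to the time of death or disease progression". A likelihood mixed model then carries a progressed patient forward from scores taken before progression, and implies a month-12 score for a patient who has died. Any worsening after progression is never recorded.

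At stake is the reading of objective 1.6. A favourable month-12 change could partly reflect who was still supplying forms, and a reader could not tell, because neither completion counts nor the target population is specified. Forms that are not collected cannot be recovered later.

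**Working it through.** **The plan's own figure.** The documents give no number for quality of life, only the denominator of 21 from the PFS design. With hazards λ0 = −ln 0.61 = 0.494 and λ1 = −ln 0.80 = 0.223, 3-year uniform accrual and 1 further year, the event probabilities 1 − (e^−λ − e^−4λ)/(3λ) are 0.682 and 0.417. On the hazard scale n = [(1.645 × 0.494/√0.682 + 0.842 × 0.223/√0.417)/(0.494 − 0.223)]² = 22.1; on the log-hazard scale it is 17.2. So 21 is reproduced within tolerance.

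**Does 7.2 stop the forms?** Under 4.1.3 pacritinib ends 21 days before conditioning, so after transplant no study drug remains to discontinue. The one-year item in the same list plainly means the end of follow-up. The 5.4.2 visits are described as specific to this study. Removal after transplant therefore most naturally ends the forms, but this is an inference.

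**Patients still event-free**, 21 × p^(m/12), exponential as in section 6.0:

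| 1-year PFS p | 1 mo | 3 mo | 6 mo | 12 mo | No month-12 form |
|---|---|---|---|---|---|
| 61% | 20.2 | 18.6 | 16.4 | 12.8 | 8.2 (39%) |
| 80% | 20.6 | 19.9 | 18.8 | 16.8 | 4.2 (20%) |

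Section 6.0 says "The historical 1-year PFS rate in this population is 61" per cent, but Table 2 shows 61% as 3-year event-free survival in the higher-dose busulfan group. If Table 2 is right, 1-year PFS is 0.61^(1/3) = 0.848, and 21 × 0.152 = 3.2 patients have an event by month 12.

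**How many of these are alive?** Take relapse as 29 of the 39 points of relapse plus non-relapse mortality (Table 2: 29% and 10%). Assume median survival after relapse of 12 months (not in the documents), so μ = ln 2 = 0.693 per year. The chance of relapse followed by death within a year is 1 − (μe^−λ − λe^−μ)/(μ − λ).

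- At 61%: 1 − (0.693 × 0.61 − 0.494 × 0.5)/(0.693 − 0.494) = 0.116. Dead: (10/39) × 0.39 + (29/39) × 0.116 = 0.187, or 3.9 of 21. Alive after progression: 8.2 − 3.9 = 4.3.
- At 80%: 1 − (0.693 × 0.80 − 0.223 × 0.5)/(0.693 − 0.223) = 0.058. Dead: (10/39) × 0.20 + (29/39) × 0.058 = 0.094, or 2.0 of 21. Alive after progression: 4.2 − 2.0 = 2.2.

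On these assumptions about half of the missing forms could be collected.

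**Bias, target all patients alive at month 12.** Assume a drop of D SD after relapse, with no earlier sign of it. The model then misses the drop entirely, and bias = D × (alive after progression)/(alive).

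- 61%: 4.3/17.1 = 0.25, so 0.125 SD (D = 0.5) or 0.25 SD (D = 1.0).
- 80%: 2.2/19.0 = 0.117, so 0.06 or 0.12 SD.

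A simulation of 4,000 patients per scenario with a random-intercept model gave 0.139 and 0.277 (61%) and 0.061 and 0.120 (80%). The excess over 0.125 and 0.25 is simulation error. With half of the drop visible in the 3 months before relapse it gave 0.088 and 0.195 (61%) and 0.048 and 0.097 (80%). The range is 0.05 to 0.28 SD.

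**Second structure.** 4,000 simulated trials of 21, random slopes (intercept SD 0.7, slope SD 0.6 per year, residual SD 0.7, all assumed), where a slope worse by 1 SD multiplies the event hazard by e^0.5 or e^1.0. The target here is the change in all 21 as if scores continued after the event.

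| PFS | Link | Observed forms only | Mixed model |
|---|---|---|---|
| 61% | e^0.5 | +0.145 | +0.124 |
| 61% | e^1.0 | +0.231 | +0.202 |
| 80% | e^0.5 | +0.072 | +0.062 |
| 80% | e^1.0 | +0.120 | +0.103 |

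With no link, the mixed-model bias was 0.002 and 0.004, within simulation error of zero. Here the mixed model removed about 13% to 15% of the bias, for example (0.145 − 0.124)/0.145 = 14%.

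**The case against.** Several stronger readings are tempting, and the objections to them stand.

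- *The month-12 result describes event-free survivors only.* It does not. The mixed model keeps the baseline, 1-, 3- and 6-month forms of patients who later progress or die. Its month-12 estimate leans on event-free patients but is not their mean.
- *The result must look too good, and the model cannot correct for it.* This is not established. Upward bias needs patients with events to do worse than their earlier scores predict. When the decline shows beforehand the model corrects part of it, and with no link the bias is nil. The documents contain no quality-of-life data.
- *7.2 certainly stops the forms.* It is a bare item in a mixed list. Under 4.1.4 patients who are not transplanted may stay on pacritinib until progression, so 7.2 may partly serve that phase. Section 5.4.2 has no progression condition, and one-year overall survival needs some follow-up after progression. That follow-up needs vital status, however, not questionnaires. If forms do continue, only deaths are lost: about 2 to 4 of 21 on the assumptions above.
- *The effect is large.* With 17 to 13 respondents and SD 1, the standard error of a mean is 1/√16.8 = 0.24 to 1/√12.8 = 0.28. The bias is at most about half a standard error at the target PFS and about one in the extreme case. This is a secondary endpoint with no stated hypothesis or decision rule, and PFS, survival and relapse are reported beside it.

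What remains after these objections is that the plan neither says whether forms continue nor defines what the month-12 change means for patients who have progressed or died.

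**Conclusion.** The point holds in limited form. Sections 5.4.2 and 7.2 must be reconciled, and the month-12 target needs a definition. On the natural reading of 7.2 and the stated PFS range, 20% to 39% of evaluable patients lack a month-12 form for reasons tied to outcome; the figure is about 15% (3.2 of 21) if 61% is a 3-year rate. A bias of roughly 0.05 to 0.28 SD in the favourable direction is plausible. It rests on assumed drops of 0.5 to 1.0 SD, or assumed links between slope and hazard, and on an assumed 12-month median survival after relapse. A reader might infer that the reported scores will necessarily show improvement; the documents do not support that, because neither direction nor size can be derived from them. The change below is a cheap improvement to a secondary endpoint, not a defect in the primary analysis.

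**What to change.** 1. State in 5.4.2 and 7.2 that the FACT-BMT and MF symptom questionnaires continue to month 12 in all living transplanted patients, including after progression, and that these forms enter the analysis.
2. For each visit report, out of all evaluable patients, the number alive, the number completing each form, and the reasons for missing forms (death, progression, other).
3. Present score change among patients alive beside the proportion alive, using a method that does not extrapolate past death, for example observed means among those alive or a model with an independence working correlation. Merely labelling the mixed model as change while alive would not achieve this, since its random effects still carry past death.
4. Keep the GLMM as planned and state its missing-at-random assumption.
5. Optionally add the proportion alive and improved, with deaths counted as not improved. This needs an improvement threshold fixed in advance, which the documents do not supply.

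Cost: a few more questionnaires from progressed patients (about 2 to 4 at month 12 on the assumptions above), short edits to 5.4.2, 7.2 and Secondary Analyses, one completion table, one further summary, and possibly a less favourable result. The sample size and the PFS analysis do not change.
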